14.6 Efficacy and Endpoint Analyses

14.6.1 Response Endpoints and Analyses

The primary efficacy endpoint is the Investigator-assessed ORR per RECIST v1.1, defined as the proportion of patients in the response evaluable population who achieve the BOR of CR or PR (called responders) per RECIST v1.1. The BOR will be categorized as CR, PR, SD, PD, or NE. To be qualified as an objective response, CR and PR require confirmation at least 4 weeks after initial observation of such response, and SD requires an observation at least once after 6 weeks. BOR will be evaluated from the start of study treatment. Number and percent of patients with their BOR will be summarized. The ORR and its 2-sided 95% exact binomial CI will be calculated for each cohort.

DCR is defined as the percentage of response evaluable patients who experienced response of CR, PR, or SD for at least 3 months. The 2-sided 95% exact binomial CI of DCR will be calculated.

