Appendix 1 Time and Events Schedule

EVALUATION/ PROCEDURE	Screening D (-28 to -1)	Cycle 1					Subsequent Cycles		EOTV ^b	Follow- Up	
		D1	D2	D3	D8 (± 1d)	D15 (± 1d)	D1 (± 3d) ^a	End of Cycle			
Enoblituzumab + retifanlimab or tebotelimab		X						X			
Informed Consent (no time constraint)	X										
Inclusion/Exclusion Criteria	X										
Demographics	X										
Medical/Cancer History	X										
Tumor biopsy ^c	X								X		
Archival tumor specimen (no time constraint) ^e	X										
HPV p16 Status (no time constraint) ^d	X										
Enrollment	X										
Physical Examination ^e	X	X						X		X	
Height	X										
Weight	X	X						X		X	
ECOG Performance Status	X	X						X		X	
ECG (12-lead) ^f	X	X									
Vital Signs ^g	X	X						X		X	
Clinical Laboratory Tests ^h	X	X						X		X	
Coagulation ⁱ	X	X									
Urinalysis ^j	X	X						X			
Pregnancy Test ^k	X	X						X		X	
Tumor Assessment ^l	X								X	X	X
Pharmacokinetics											
ADA											
PBMCs, Serum, and Plasma for PD and Exploratory Biomarkers											
Concomitant Medications											
Concomitant Procedures											
Adverse Events											
Survival											X ^m

*In clinic visit for
PK/ADA/biomarker
assessments only*

See [Appendix 3](#)

See [Appendix 3](#)

See [Appendix 3](#)

EVALUATION/ PROCEDURE	Screening D (-28 to -1)	Cycle 1					Subsequent Cycles		EOTV ^b	Follow- Up
		D1	D2	D3	D8 (± 1d)	D15 (± 1d)	D1 (± 3d) ^a	End of Cycle		

- a A cycle is 21 days ± 3 days from the previous dosing day. There should be at least 18 days between administrations.
- b The EOTV, if conducted, should be performed within 30 days after the patient has met study treatment discontinuation criteria specified in [Section 4.4](#), and before initiation of any subsequent anticancer therapies.

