- j Urinalysis (see [Appendix 2](#)) performed at screening, Day 1 of each cycle (with a window of -3 days in relation to the beginning of each cycle), and as clinically indicated.
- k Serum or urine pregnancy test for women of child-bearing potential (with a window of -3 days in relation to the beginning of each cycle).
- l Tumor assessments are performed at the end of Cycle 2 (with a window of -3 days in relation to the beginning of the next cycle), and at the end of every 3 cycles (Cycles 5, 8, 11, etc.) thereafter (with a window of -7 days in relation to the beginning of the next applicable cycle) until treatment discontinuation. Patients who discontinue from study treatment should be assessed every 12 weeks (± 1 week) after the EOTV (or, if no EOTV is conducted, after the decision to end treatment) until evidence of PD, initiation of another anticancer therapy, withdrawal of consent, LTFU, death, or 36 weeks after the last patient's EOTV. EOTV tumor assessment does not need to be conducted if prior tumor assessment was performed within 28 days of the EOTV and results are available for RECIST assessments. Patients who discontinue study treatment due to AEs are followed by radiographic evaluation until PD by RECIST v1.1, if the patients' condition allows. If not, patients will be followed for OS without radiographic evaluation upon the discussion with the Sponsor's Medical Monitor.
- m Survival follow-up occurs every 12 weeks (± 1 week) after the EOTV (or, if no EOTV is conducted, after the decision to end treatment) until withdrawal of consent, LTFU, death, or 36 weeks after the last patient's EOTV.

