2.4.3 Best overall response: all time points

The *best overall response* is determined once all the data for the patient is known.

Table A-1 Time point response: patients with target (+/- non-target) disease

Target lesions	Non-target lesions	New lesions	Overall response
CR	CR	No	CR
CR	Non-CR/non-PD	No	PR
CR	Not evaluated	No	PR
PR	Non-PD or not all evaluated	No	PR
SD	Non-PD or not all evaluated	No	SD
Not all evaluated	Non-PD	No	NE
PD	Any	Yes or No	PD
Any	PD	Yes or No	PD
Any	Any	Yes	PD

CR = complete response, PR = partial response, SD = stable disease, PD = progressive disease, and NE = inevaluable.

Best response determination in trials where confirmation of complete or partial response IS required: Complete or partial responses may be claimed only if the objective response is confirmed on a follow-up scan obtained no less than 4 weeks after the initial scan demonstrating an objective response. In this circumstance, the best overall response can be interpreted as in **Table A-2**.

Table A-2 Best overall response when confirmation of CR and PR required

Overall response First time point	Overall response Subsequent time point	BEST overall response
CR	CR	CR
CR	PR	SD, PD or PR ^a
CR	SD	SD
CR	PD	SD
CR	NE	SD
PR	CR	PR
PR	PR	PR
PR	SD	SD
PR	PD	SD provided minimum criteria for SD duration met, otherwise, PD
PR	NE	SD provided minimum criteria for SD duration met, otherwise, NE
NE	NE	NE

CR = complete response, PR = partial response, SD = stable disease, PD = progressive disease, and NE = inevaluable.

- a. If a CR is *truly* met at first time point, then any disease seen at a subsequent time point, even disease meeting PR criteria relative to baseline, makes the disease PD at that point (since disease must have reappeared after CR). Best response would depend on whether minimum duration for SD was met. However, sometimes ‘CR’ may be claimed when subsequent scans suggest small lesions were likely still present and in fact the patient had PR, not CR at the first time point. Under these circumstances, the original CR should be changed to PR and the best response is PR.

Special notes on response assessment

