2.5.3 Duration of stable disease

Stable disease is measured from the start of the treatment until the criteria for progression are met, taking as reference the *smallest sum on study* (if the baseline sum is the smallest, this is the reference for calculation of PD).

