5 ENDPOINTS

5.1 Efficacy Endpoints

5.1.1 Primary Efficacy Endpoints

The primary efficacy endpoint is the Investigator-assessed ORR per Response Evaluation Criteria in Solid Tumours version 1.1 (RECIST v1.1), defined as the proportion of patients in the response evaluable population who achieve the best overall response (BOR) of complete response (CR) or partial response (PR) (called responders) per RECIST v1.1. The BOR will be categorized as CR, PR, stable disease (SD), progressive disease (PD), or not evaluable (NE). To be qualified as an objective response, CR and PR require confirmation at least 4 weeks after initial observation of such response, and SD requires an observation at least once after 6 weeks. BOR will be evaluated from the start of study treatment.

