5.1.2 Secondary Efficacy Endpoints

The secondary efficacy endpoints are:

- PFS assessed by Investigator, defined as the time from the first dose date to the date of first documented progression or death from any cause, whichever occurs first. The documented progression is determined by objective assessment of disease per RECIST v1.1. For patients who are not known to be dead or progressed at time of data cut-off for PFS analysis, the PFS will be censored at the date of the last tumor assessment. Specifically, the following censoring rules will be applied ([Table 2](#)).
 - $\text{PFS (months)} = (\text{date of event [documented progression or death] or date of censoring} - \text{date of first dose} + 1) / (365.25/12)$

Table 2 Censoring Rules for PFS Analysis

Situation	Date	Outcome
No baseline tumor assessments	First dose date	Censored
Death prior to first scheduled tumor assessment	Date of death	Progressed
No post-baseline tumor assessments in absence of death prior to first scheduled tumor assessment	First dose date	Censored
Documented progression	Date of progression	Progressed
Initiation of alternative anti-cancer treatments in absence of documented progression	Date of last tumor assessment prior to initiation of such treatment	Censored
Death or documented progression immediately after missing 2 or more consecutive scheduled tumor assessments	Date of last tumor assessment prior to missed assessments	Censored

- DoR, defined as the time from the date of initial response (CR or PR) to the date of first documented progression per RECIST v1.1 or death from any cause, whichever occurs first. The DoR is calculated only for the responders. For responders who are not known to be dead or progressed at the time of data cut-off for DoR analysis, the DoR will be censored at the date of the last tumor assessment. Specifically, the last 3 situations described in **Table 2** will be applied. The DoR analyses will be performed only if there are enough responders to render the analyses meaningful.
 - $\text{DoR (months)} = (\text{date of event [documented progression or death] or date of censoring} - \text{date of initial response} + 1) / (365.25/12)$
- DCR, defined as the percentage of response evaluable patients who experienced response of CR, PR, or SD for at least 3 months.

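### The six-week minimum for stable disease as best response rejects first scans taken on schedule, and conflicts with the stable-disease duration rule that bears on DCR

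*SAP*

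**What the plan says.** Best overall response is defined in SAP 5.1.1, with the same rule in Protocol 14.6.1. For stable disease both state: "SD requires an observation at least once after 6 weeks".

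The scan calendar is in Protocol Appendix 1, footnote l. The first assessment is "at the end of Cycle 2 (with a window of -3 days in relation to the beginning of the next cycle"; later ones come "at the end of every 3 cycles (Cycles 5, 8, 11, etc.) thereafter (with a window of -7 days". Both windows run backwards only. Footnote a fixes cycle length: "A cycle is 21 days ± 3 days from the previous dosing day", with at least 18 days between doses.

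SAP 5.1.2 defines the secondary endpoint: "DCR, defined as the percentage of response evaluable patients who experienced response of CR, PR, or SD for at least 3 months". Protocol 14.6.1 has the same definition. Neither sentence says how the 3 months are timed. Protocol Appendix 4, section 2.5.3, does give a rule: "Stable disease is measured from the start of the treatment until the criteria for progression are met".

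**The concern.** The minimum for SD and the window for the scan meant to show SD do not fit together. The earliest planned scan falls at or before six weeks, while the rule asks for an observation after six weeks. The next planned scan is nine weeks later. A patient who is stable at the first scan and has progressed by the second therefore has no SD observation that satisfies the rule, although every scan was on schedule.

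Two reported results depend on this. One is the best-response table, where the patient moves from SD to PD or NE. The other is DCR, because the documents do not say whether SD in that endpoint means SD as best response (with the six-week minimum) or SD timed by section 2.5.3. Under the second rule the patient can be counted as disease-controlled while the first lists the same patient as PD.

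**Working it through.** The plan gives no figure for SD or DCR to reproduce. Its design figures concern ORR and do reproduce: with n = 50 and at least 14 responses, the exact binomial probability is 0.0791 at a true rate of 19% and 0.9097 at 36%, matching the stated 0.079 and 91%. SD enters neither.

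**Inputs.** Let c be the mean cycle length in days: 21, with 18 to 24 allowed (Protocol Appendix 1, footnote a). Six weeks = 42 days. One month = 365.25/12 = 30.4375 days (the SAP 5.1.2 conversion), so 3 months = 91.3 days.

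**Scan days after first dose, without dose delays.** First scan: 2c - 3 to 2c. Second scan: 5c - 7 to 5c.

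| c | First scan | Second scan |
|---|---|---|
| 18 | 33-36 | 83-90 |
| 21 | 39-42 | 98-105 |
| 24 | 45-48 | 113-120 |

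**Six-week test.** A scan on Cycle 3 Day 1 is later than day 42 only if 2c > 42, so c > 21. A scan 3 days early passes only if 2c - 3 > 42, so c > 22.5. At 21-day cycles no compliant first scan passes. More lenient counting rescues only part of the window. If exactly 42 days is accepted, and the SAP's extra day is added as for PFS (days 39-42 become 40-43), scans on Cycle 3 Day 1 or one day before pass, but scans 2 or 3 days early still fail.

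**Best response.** With the minimum not met, SD followed by PD becomes PD, and SD with no later scan becomes NE. Protocol Appendix 4, Table A-2, spells this out for an unconfirmed PR followed by PD: "SD provided minimum criteria for SD duration met, otherwise, PD". The same logic carries over to a first reading of SD.

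**Duration under section 2.5.3.** For SD at the first scan and PD at the second, with c = 21: 98/30.4375 = 3.22 months and 105/30.4375 = 3.45 months. Adding the SAP's extra day gives 3.25 to 3.48. All exceed 3 months, so the patient qualifies for DCR while best response is PD. At c = 18 the range is 83/30.4375 = 2.73 to 90/30.4375 = 2.96 months: the patient misses both criteria and the rules agree. At c = 24 the first scan passes the six-week test and the rules agree again. The conflict therefore sits at and around the planned 21-day cycle.

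**Size per patient.** 1/50 = 2.0 points in the Retifanlimab Cohort; 1/30 = 3.3 points in the Tebotelimab Cohort.

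**Illustration (assumed shares, not in the documents).** Suppose 10% or 20% of patients have SD on the first scan only, and DCR without them is 30%. Counting them moves DCR as follows (exact 95% CI):

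- n = 50: from 15/50 (17.9-44.6%) to 20/50 (26.4-54.8%) or 25/50 (35.5-64.5%).
- n = 30: from 9/30 (14.7-49.4%) to 12/30 (22.7-59.4%) or 15/30 (31.3-68.7%).

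**The case against.** The best defence is intent. Protocol 4.1 and SAP 3.1 place the first scan at approximately six weeks, so the authors surely meant that scan to be able to establish SD. That is probably right, and it is why a sentence is enough. But the minimum itself carries no such tolerance, and a program needs a number. The statistical programming plan, not available here, may supply one; an endpoint definition still belongs in the SAP. It is also true that DCR is descriptive, with no test or threshold attached.

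Some stronger readings are tempting but not supported:

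- A reader might infer that the plan has no end rule for SD, so that SD at week 6 with PD at week 15 is indeterminate for DCR. Section 2.5.3 supplies the rule, and under it that patient counts at 21-day cycles. What is missing is a citation of it in the DCR definition.
- A reader might infer a large swing in DCR by ending SD at the last scan without progression. No passage times SD that way when progression is documented, and any such size would rest on an assumed PFS curve and on how much early progression is dated before day 91.
- A reader might conclude that DCR should become disease control at the end of Cycle 5. That would accept a scan as early as day 83, below 3 months, and drop patients who had 3 months without progression but progressed by that scan.
- A reader might apply the 3 months to CR and PR as well. The phrase attaches most naturally to SD.

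**Conclusion.** The point holds as a mismatch between two rules. At 21-day cycles the six-week minimum, read as written, is met by no compliant first scan, and on the most lenient counting it still excludes scans taken 2 or 3 days early. A patient with SD only on that scan is then reported as PD or NE, while section 2.5.3 can credit the same patient with enough SD for DCR.

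The effect is confined to the SD, PD and NE counts in the best-response table and to the descriptive DCR. The change per patient is certain; the number of patients is not, and the 10% and 20% shares above are assumptions. ORR, the 14-of-50 criterion, the type I error and the power do not change. The conclusion assumes that the programming plan contains no tolerance for the first scan.

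**What to change.** In SAP 5.1.1 and Protocol 14.6.1, add one sentence: SD on the end-of-Cycle-2 assessment, taken within its allowed window, meets the minimum for SD. Give the number: at least 33 days from first dose, which covers the permitted 18-day intervals, or at least 39 days if only 21-day cycles are assumed.

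As a minor clarification in SAP 5.1.2:

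- cite Protocol Appendix 4, section 2.5.3, as the SD duration rule for DCR;
- for patients who die without documented progression, start new anticancer therapy or are lost to follow-up, end SD at the last evaluable scan and keep them in the denominator;
- state that the 3 months apply to SD only.

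The cost is wording; no scan or visit is added. Slightly shorter SD is accepted as best response. A patient whose only SD scan is the first, and who then dies without documented progression or is lost, will not reach 3 months and counts as not controlled.

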5.1.3 Other Efficacy Endpoints

Tumor size change over time will be calculated. The tumor size is defined as the sum of diameters of the target lesions.

5.2 Safety Endpoints

5.2.1 Adverse Events

Safety will primarily be addressed by evaluations of the adverse events (AEs). AE is defined as any untoward medical occurrence in a patient or clinical trial patient associated with use of a drug in humans, whether or not considered drug related. An AE can be

- any unfavorable and unintended sign (including an abnormal laboratory finding, for example), symptom, or disease temporally associated with the use of a medicinal product, whether or not considered related to the medicinal product.
- any occurrence that is new in onset or aggravated in severity or frequency from baseline condition, or abnormal results of diagnostic procedures, including laboratory test abnormalities.

All AEs whether serious or non-serious, will be reported from the time a signed and dated informed consent form (ICF) is obtained until 30 days following the last dose of study drug or until the start of a subsequent systemic anti-cancer therapy, if earlier. AEs will be coded using the latest version of Medical Dictionary for Regulatory Activities (MedDRA). An assessment of severity grade will be made using NCI-CTCAE v5.0.

Both protocol-related AEs and serious adverse events (SAEs) will be collected from the time the patient has consented to study participation. AEs and SAEs reported between the time the patient signs the ICF and the administration of the first dose of study drug will be captured as concurrent medical history unless the events are attributed to protocol-specified procedures. Events attributed to protocol-specified procedures will be collected on the Adverse Event eCRFs and SAE Report form as appropriate.

Only treatment emergent adverse events (TEAEs) will be summarized as safety endpoints. A TEAE is defined as any event that is newly occurring on or after the administration of study drug or an event that existed before but increased in severity on or after study drug administration.

5.2.2 Laboratory Evaluations

Central laboratory testing should be used to determine patient eligibility and assess overall safety in the study, unless the Medical Monitor approves the use of a local laboratory in place of an unanalyzable central laboratory sample. Local laboratories will be used for clinical decision making. A laboratory abnormality is reported as an AE if any criterion for an SAE is fulfilled, or the event is associated with an intervention including, but not limited to, discontinuation or interruption of treatment, dose reduction/delay, or required initiation of concomitant therapy. Also, any laboratory abnormality may be reported as an AE at the Investigator's discretion, based on clinical significance.

5.2.3 Other Safety Endpoints

Physical examination will be performed (including weight and height) for all patients according to the schedules outlined in the protocol.

Vital signs (include temperature, pulse, blood pressure, and respiratory rate) and Eastern Cooperative Oncology Group (ECOG) performance status will be performed according to the schedules outlined in the protocol.

Twelve-lead electrocardiograms (ECGs) will be obtained according to the protocol to evaluate the potential cardiac effect. Screening and Cycle 1 Day 1 ECGs are performed in triplicate. Subsequent ECGs are obtained as clinically indicated. ECG baseline is defined as the average of the last assessment with replicates taken before first dose of study treatment.

5.3 Pharmacokinetic, Pharmacodynamic, and Immunogenicity Parameter Endpoints

PK samples, immunogenicity (ADA) samples and pharmacodynamic biomarker specimens will be collected according to the schedules outlined in the protocol.

Prospective PD-L1 testing will be performed for all patients. PD-L1 protein expression is determined by using CPS, which is the number of PD-L1 staining cells (tumor cells, lymphocytes, macrophages) divided by the total number of viable tumor cells, multiplied by 100. The specimen should be considered to have PD-L1 expression if $CPS \geq 1$. PD-L1 expression will be assessed based on immunohistochemistry (IHC) staining using the FDA-approved 22C3 pharmDx assay.

IHC to assess B7-H3 expression will be performed in all patients. PD-1/LAG-3 testing will be performed by PD-1 and LAG-3 dual IHC staining. These biomarker assessments will be prospectively collected and retrospectively analyzed.

Local laboratory results are acceptable for evaluation of human papilloma virus (HPV) p16 status.

6 STATISTICAL METHODOLOGY

6.1 General Considerations

Safety and efficacy summaries will be provided for each cohort.

Unless otherwise noted, the baseline value is defined as the most recent value collected prior to the date and time of the first dose of study treatment. Study Day 1 is defined as the first day of study drug administration.

Categorical data will be summarized by the number and percent of patients falling within each category. Continuous variables will be summarized by descriptive statistics, including mean, standard deviation, median, minimum, and maximum.

Time to event endpoints will be summarized by the number and percent of the event, median time and corresponding 95% confidence interval (CI), and event free rate and corresponding 95% CI at the specified time points of interest.

All data summaries and tabulations will be conducted using SAS[®] software Version 9.4 or higher.

6.2 Missing Data

Data that are reported as missing will be treated as missing in all data summaries. Imputation rules for partially recorded dates, where complete dates are required to carry out an analysis, will be provided in the Statistical Programming Plan (SPP). In descriptive summaries for safety, observations that are spurious (extreme relative to the majority of the data) will not be altered or removed from the summary.

6.3 Patient Disposition and Baseline Characteristics

6.3.1 Patient Disposition

For patient disposition, the number and percentage of patients who reach various study milestones are summarized. All screened patients are broken down by screen failures (with reasons if collected) and enrolled. Then the category of enrolled is broken down by never treated (with reasons if collected) and treated. The category of treated will further be broken down by treatment ongoing and treatment discontinuation (with reasons for discontinuation, which also include protocol-defined treatment completion, if any). The end of study status for all enrolled patients will also be included.

